4.3 End of Study

End of study is defined as the date of the final interview of participants in work package 3.

4.4 Schedule of Procedures

Work Package 2 (WP2):

Procedures	Visits				
Procedures	Baseline	Week 2*	Week 6*	Week 12*	
Informed consent	Х				
Demographics	х				
Intervention training	Х	x if required			
VAS / KOOS-PF	Х	х	Х	х	
Adverse Events		х	х	Х	
Observation of treatment		х			
Feedback on treatment		х	x	Х	
Telephone/online assessment			х	х	
WP3 Interview discussion				х	

^{*+/- 5} days

Work Package 3:

Procedures	
Flocedules	Single visit
Informed consent	x
Face to face, telephone or online interview	x

4.6 Device in Use

The sports medical tape for this trial is widely used in UK clinical practice and is FDA approved and CE-marked. The tape is approved for use for the treatment of knee pain. It is budgeted for purchase within the study funding stream. Purchase orders will be raised by MFT, product will be shipped, once invoices are paid, to the Stopford Building/or Manchester CRF building and received by the Goods-In Department and delivered to the study team. Sufficient tape will be cut and distributed to the participants at the baseline and 2 weeks visits by the CI along with in person training plus the training materials submitted alongside this protocol. Any excess tape will be disposed of in general waste by the participants at home, information is in the PIS. The advice given will be that participants

should try and wear the tape for as long as is comfortable and taken off at night to be applied fresh the following day. There are no known complications with other treatments being used at the same time.

Manufacturer: We Tape

Brand: Rocktape UK: https://www.rocktape.co.uk

Distributer: c/o Fit Brands Ltd, [name]

This product is a class I medical device and is CE Marked. The CE mark is clearly visible on the outside of the packaging.

The product is made from 97% cotton and 3% nylon, it is hypoallergenic and it does not contain latex.

5. Study Sample and Recruitment

5.1 Eligibility Criteria

All individuals will be considered for inclusion in this study regardless of age, disability, gender reassignment, marriage and civil partnership, pregnancy and maternity, race, religion and belief, sex, and sexual orientation except where the study inclusion and exclusion criteria EXPLICITLY state otherwise.

5.1.1 Inclusion Criteria

- Adults of any gender aged 40 years of age or over.
- Pain predominantly over the patella (anterior knee pain) and greater than medial or lateral compartment knee pain.
- Clinically significant patellofemoral pain / anterior knee pain on weight bearing activity such as stair ascent/descent, sit-stand-sit scored at 4 or above on an 11 point (0 no pain–10 worst pain) visual analogue scale (VAS).
- Already on a stable/regular dose of analgesia.
- Able to understand English (or English speaking) and give full informed consent.
- Willing to participate.

5.1.2 Exclusion Criteria

- Symptoms not attributable to predominant patellofemoral OA or attributable only medial or lateral knee compartment OA.
- Previous major surgery in the knee to be treated (partial/total knee replacement, knee fracture or knee realignment surgery, high tibial osteotomy).
- Diagnosis of rheumatoid arthritis, gout or other forms of inflammatory arthritis.
- Cancer within the last 5 years (except non-melanoma skin cancers).
- Planned knee replacement surgery or other knee surgery in the next 6 months.
- Responded to a steroid or viscosupplementation injection to the painful knee in the last 3 months.
- Those with a known allergy to elasticated tape, with fragile or very sensitive skin, psoriasis, or with lesions/rash/open wound in the area where the tape will be applied.
- Significant neurological disorder (e.g. stroke, dementia, MS, Parkinson's) or affecting cognitive ability.

5.2 Study Setting and Sample Identification

Participants will be identified by [name] and clinical team at the Manchester Local Care Organisation (MLCO) or by [name] in clinics at Salford Royal Hospital. Participants will be given a PIS to read and consider.

Those who are interested in taking part will be invited to attend a face-to-face baseline visit at the NIHR Manchester Clinical Research Facility. At the baseline visit potential participants will be asked to confirm that they have received and read this PIS. The researcher will further discuss the study with the potential participant and give an opportunity for them to ask questions.

If recruitment is not met by the above clinics an advert will be posted on the University of Manchester intranet and in the Manchester Evening News. This will invite potential participants to scan a QR code which leads them to some basic questions about their knee health and skin condition. If they are suitable, they will be given details to contact the research team.

The assessment and delivery of WP2 will take place in the NIHR Manchester Clinical Research facility. Participants will self-apply the taping intervention in their homes. The delivery of WP3 will take place in the Department of Health Professions at [name], Manchester Metropolitan University. Participants will be purposefully selected from those in the WP2 arm who have completed the 12 weeks programme by the CI and [name] from the Manchester Metropolitan University.

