3.2 Outcome Measures

Primary outcome

 WP2: To assess recruitment to the study and retention: Participant uptake – number of participants recruited and number of participants who complete the study.

WP3: Report on participant experiences of taping and the trial process. Explore facilitators and barriers to adherence. Evaluate the performance of the participant treatment package.

Secondary outcomes (ii - vii)

- ii) To determine whether the tape can be applied by participants correctly at home: Clinical checks at 2 weeks recorded on the Clinical Report Form.
- iii) Adherence:
 - a. Number of returned or counted unused tapes
 - b. Number of days since the previous timepoint that participants report wearing the tape collected at weeks 2, 6 and 12.
 - c. Average number of hours the participants report wearing the tape daily since the previous timepoint at weeks 2, 6 and 12.
- (iv & v) To assess how to optimise adherence of taping over an extended period and to determine participants views about the acceptability of prolonged taping: Participants interviews in WP3.
- (vi) Effect of intervention: Reduction in pain

- (a) Knee pain measured by VAS_{NA} at baseline, 2, 6 & 12 weeks.
- (b) Knee pain and function measured by KOOS-PF at baseline, 2, 6 & 12 weeks.
- (vii) To determine a primary outcome for a large scale RCT and to inform sample size calculation: Analysis of quantitative data in vi a & b

4. Study Design and Methods of Data Collection

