Participants completing WP2 will all be given a PIS for WP3 and asked if they are interested in taking part in WP3. It will be explained that they may not be picked, depending on how many say yes as we will only require fifteen. Fifteen participants from the feasibility trial (WP2) will be invited to participate in one-to-one semi-structured interviews for WP3. Participants will be purposively recruited from those who consented to be contacted in WP2, to reflect a range of sex, age and ethnicity. It is anticipated that this sample size will be sufficient to generate rich data. However, recruitment will continue until data saturation has been achieved. Moreover, if data saturation is achieved before recruiting the fifteenth participant, recruitment will be stopped at that point. Purposive recruitment will allow us to include the voices of participants not commonly heard in this type of research, including those from underserved communities. As such, we are confident that purposively recruiting 15 participants is appropriate for this study. Semistructured interviews of approximately 60 minutes will be conducted to gain in-depth understanding of participants' experience of the intervention. Interviews will be informed by an interview guide developed from the findings of WP1, the research team including PPIE representative, underpinned by the Theoretical Framework of Acceptability (21) (see appendix 1). Participants will be interviewed by the research associate (RA) who is trained in undertaking qualitative interviews either in-person, online via Teams, or over the phone depending on the participants' preference. In-person interviews will take place in a private room at the [name], Manchester Metropolitan University. Two participants who will have taken part in the clinical trial will pilot the guide to ensure its appropriateness. Consent and demographic information will be collected at the start of the interview. Further discussion will be guided by each participant's response to the questions to allow exploration of unanticipated issues. Emerging findings from each interview will iteratively feed into subsequent interviews. Interviews will be digitally recorded, and interviews will be professionally transcribed.

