5.5 Consent

Subjects will be asked to sign an informed consent form in the presence of the CI prior to taking part in any study procedures. As part of the informed consent process, participants will have been given a PIS to read for at least 24 hours. At the baseline visit, participants will have the opportunity to ask any questions, discuss the research and their involvement before they decide.

At the last visit of WP2, participants will be asked if they would like information to take part in follow-up interviews to explore their experiences of the trial and intervention acceptability in WP3. Further PIS for WP3 will be provided at this stage.

WP3 may take place purely online (via Teams) or by telephone, therefore copies of the consent form will be sent and returned with scanned or e-signatures via email or through the post in pre-paid envelopes.

Data protection and confidentiality measures taken by the CI and the host institution will be explained to the participant.

It will also be explained that participants are free to withdraw consent at any time without giving any reason, and without their legal rights being affected. All data collated up to the point of withdrawal will be retained for use with the analysis.

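### WP3 interviews are open only to participants who complete WP2, so anyone who leaves or is withdrawn before week 12 has no route to interview on barriers and acceptability

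*Protocol*

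**What the plan says.** Section 5.2 of the protocol defines the WP3 frame: "Participants will be purposefully selected from those in the WP2 arm who have completed the 12 weeks programme". Section 4.2 describes the invitation in similar terms: "Participants completing WP2 will all be given a PIS for WP3 and asked if they are interested in taking part in WP3". Section 5.5 fixes the moment: "At the last visit of WP2, participants will be asked if they would like information to take part in follow-up interviews". The flow chart puts the interview invitation after the end of WP2, and the schedule in section 4.4 puts the WP3 discussion at week 12.

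Section 4.2 also has a looser phrase: "Participants will be purposively recruited from those who consented to be contacted in WP2". The purposive criteria given there are demographic: "to reflect a range of sex, age and ethnicity". Adherence, withdrawal and response to tape are not among them.

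The Study Summary and section 3.2 place the WP3 report under the primary outcome, with this content: "Explore facilitators and barriers to adherence. Evaluate the performance of the participant treatment package". Section 3.2 names the WP3 interviews as the source for objectives iv and v, both secondary. Section 7.1 says that a participant with any skin irritation, even slight, is withdrawn from the trial.

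**The concern.** The interviews are meant to explain why people do or do not keep using the tape, but the frame depends on staying in the trial. Leaving early may itself result from the barriers being studied. The protocol's rationale sharpens this: its previous brace trial was held back by poor tolerance and wearability (sections 1 and 2), and early leavers are well placed to say whether taping has a similar problem.

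Saturation does not guard against this. It is judged among the people interviewed, so a completers-only sample can saturate without any account from someone who left. Willingness to be randomised is also explored in the interviews (section 4.2 and Appendix 1), so that information for the future RCT comes from the same group.

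**Working it through.** The protocol gives no figure for this point, so the check is mainly a comparison of sections, followed by the size of the group left out.

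**1. Is there any route to interview for a leaver?**

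| Place | Who or when |
|---|---|
| 4.2 | Information sheet goes to those completing WP2 |
| 5.2 | Selection from those who finished the 12-week programme |
| 5.5 | Approach at the last WP2 visit |
| Flow chart | Invitation after WP2 ends |
| 4.4 | WP3 discussion at week 12 |

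All five agree. The phrase in 4.2 about consent to contact does not open another route, because the same paragraph offers the WP3 information sheet to completers. No section describes an approach to someone who withdraws, is withdrawn or is lost.

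**2. Who is clearly outside, and who is uncertain?**

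- Clearly outside: people who leave or are withdrawn before week 12, including those withdrawn under section 7.1 for a skin reaction.
- Uncertain: people who stop taping but still take the week 12 call. They can be read as completing WP2 (4.2), but perhaps not as completing the programme (5.2).

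**3. Size.** Inputs: N = 30 and drop-out d = 20% (section 5.3.1); 15 interviews (section 4.2). The values d = 10% and 30% are assumed, to show a range.

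- Number leaving = 30 × d; at 20% this is 30 × 0.20 = 6, which leaves 24 who can be invited.
- Leavers among the 15 interviews under the current frame = 0.
- For comparison only, if 15 were drawn at random from all 30: expected leavers = 15 × d, and P(at least one) = 1 − C(30 − k, 15)/C(30, 15), with k the number of leavers.

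| d | k leaving | Expected in a random 15 | P(at least one) |
|---|---|---|---|
| 10% (assumed) | 3 | 1.5 | 0.89 |
| 20% (protocol) | 6 | 3.0 | 0.99 |
| 30% (assumed) | 9 | 4.5 | >0.99 |

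WP3 sampling is purposive, and some leavers would decline or be unreachable, so the last two columns do not forecast what an open frame would yield. They show that the absence of leavers comes from the rule and not from the small number of interviews.

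**4. Link to the progression table.** Section 4.2 sets the middle band for loss to follow-up at 10% to 20%, which is 3 to 6 of 30. In that band the design would be edited, and reasons for leaving would be most useful.

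**The case against.** The other side has several good points, and they limit the claim.

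- **Stopping tape is not the same as leaving the study.** A reader might infer that everyone who stopped is excluded. The documents do not support that. WP2 follow-up records days and hours worn and counts unused strips, so it expects low users, and someone who stopped but stayed in contact may count as completing WP2.
- **Reasons for stopping are partly collected.** A reader might infer that they go entirely unrecorded. Section 6.1 gathers reasons for unused tape at weeks 2, 6 and 12, section 4.4 schedules treatment feedback at the same contacts, and section 4.2 collects adverse events at each contact. Where someone is withdrawn for a skin reaction, that reason is known. These data do not, however, give interview depth from people who have left.
- **Acceptability is not itself a primary outcome.** It is secondary objective v. Experiences, facilitators and barriers, and the performance of the package are what sit under the primary heading.
- **No percentage bias can be derived.** It is tempting to compare an acceptability rate in completers with one in all recruited participants. WP3 is an inductive thematic analysis and estimates no such proportion, and the documents give no rates to put in. The related progression measure, willingness to use the tape again, is defined on recruited participants.
- **Not all 6 are lost because of the rule.** The 20% is an allowance for drop-out of every kind. Some would be unreachable or refuse under any frame, and some may leave for reasons unrelated to tape.
- **The existing criteria have a rationale.** Section 4.2 wants to hear underserved voices. That is sound, and adding a criterion does not displace it.

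None of this supplies a route to interview for people who leave or are withdrawn early.

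**Conclusion.** The point holds in a limited form. As written, WP3 cannot interview anyone who leaves or is withdrawn before week 12, although it is the source for barriers to adherence (under the primary outcome) and for secondary objectives iv and v. The group is up to about 6 of 30 at the protocol's 20% drop-out, or 3 to 9 if drop-out were 10% to 30% (assumed). The number who could in practice be recovered is smaller and unknown.

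The likely consequence is a qualitative account tilted towards people who tolerated the tape. The direction rests on the assumption that at least some leave because of the tape; section 7.1 makes this certain for anyone who develops a skin reaction. The size of the tilt cannot be stated. The eligibility of people who stop taping but remain in follow-up is an ambiguity to settle, not a demonstrated exclusion. This is a cheap improvement that should be made before recruitment, because leavers are hard to recover later.

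**What to change.** Amend sections 4.2, 5.2 and 5.5 together, with the flow chart and schedule to match:

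1. Offer the WP3 information sheet to every recruited participant who agrees to be contacted. For those who withdraw or are withdrawn, do so at the time they leave.
2. State that people who stop taping but remain in follow-up are eligible, and use one definition of the frame throughout.
3. Add adherence or withdrawal status to sex, age and ethnicity as a purposive criterion. No fixed quota is needed, and none can be derived from the documents.

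The planned number of interviews stays at about 15. This concerns sampling only and leaves the withdrawal rule in section 7.1 as it is. Adding a question to the week 12 call would not cure the selection, because those who have left are not on that call.

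The cost is a protocol amendment and a change in when the information sheet is given. The documents do not say whether this would be classed as substantial; if so, section 7.3 requires REC and HRA approval first. Leavers may also be harder to recruit, so the report should state how many were approached and how many were interviewed.

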5.3 Sampling

5.3.1 Size of Sample

This is a pragmatic sample size calculation for a feasibility study. A sample size of 30 is sufficient to allow estimation of feasibility parameters with 95% confidence intervals, including a drop out of 20% (19). A target of 50% for the primary outcome, participant uptake, can be estimated with 95% confidence intervals 36.8-63.2%.

5.4 Recruitment

Central Manchester has a diverse ethnic and socio-economic population. Based on previous trials we would expect the diversity of the population to be reflected in our recruitment. Two recruitment methods will be used for WP2.

- 1. Musculoskeletal physiotherapy practitioners from the Manchester Local Care Organisation (MLCO) will refer participants with PFJOA from clinics using, preferably the online NHS Trust research referral pathway (HIVE). If this is not available, then participants will be directly referred using the Study Team's secure NHS or NHS.net email address. Potential participants will be given a participant information sheet (PIS) with study details and an invitation to contact the trial team by email or telephone visit. If, after talking with the trial team, they are still interested they will be invited to attend for a face-to-face screening baseline visit.
- 2. Participant Identification Centre: Salford Royal Hospital [name] will act as a collaborator to identify potential participants from musculoskeletal clinics. The referral method would then be as method 1 above with the MLCO with potential participants being offered a participant information sheet (PIS) with study details and an invitation to contact the trial team by email or telephone.
- 3. Subjects will be recruited through advertisements on the university websites / online and print news media. Potential participants will be invited in these advertisements to scan a QR code that leads them to some questions about their knee health and skin conditions. The questions have been informed by our previous work to identify those likely to have PFJOA; this is estimated to take about 15 minutes. Participants who are interested in taking part and where there are no obvious exclusions (e.g. age, recent knee surgery, poor skin condition around the test site) will be given details to contact

the research team and be sent a PIS. If, after reading the PIS, they are still interested they will be invited to attend for a face-to-face baseline visit.

5.5 Consent

Subjects will be asked to sign an informed consent form in the presence of the CI prior to taking part in any study procedures. As part of the informed consent process, participants will have been given a PIS to read for at least 24 hours. At the baseline visit, participants will have the opportunity to ask any questions, discuss the research and their involvement before they decide.

At the last visit of WP2, participants will be asked if they would like information to take part in follow-up interviews to explore their experiences of the trial and intervention acceptability in WP3. Further PIS for WP3 will be provided at this stage.

WP3 may take place purely online (via Teams) or by telephone, therefore copies of the consent form will be sent and returned with scanned or e-signatures via email or through the post in pre-paid envelopes.

Data protection and confidentiality measures taken by the CI and the host institution will be explained to the participant.

It will also be explained that participants are free to withdraw consent at any time without giving any reason, and without their legal rights being affected. All data collated up to the point of withdrawal will be retained for use with the analysis.

5.6 Participant Compensation

We will offer £70 per participant as a thank you for peoples' time and effort at the end of Work Package 2. This is for 2 face-to-face visits and 2 online/telephone calls.

We will offer £25 per participant as a thank you for time and effort for Work Package 3.

6. Statistics and Analysis

6.1 Data Analysis

Intervention arm WP2:

All variables will be examined using appropriate descriptive statistics (mean [standard deviation], median [interquartile range], n [%]) and graphics for completeness and form. No imputation will be made for missing data, however quantities and location will be used to inform the design of a future RCT.

The primary outcome, recruitment rate, will be presented as a proportion with 95% binomial confidence intervals. This will also be presented on a monthly basis. Other feasibility parameters, dropout rates and those with complete data, will be presented similarly.

Adherence, i.e. number of returned tapes and the number of days and average hours of daily usage, will be reported for each timepoint as continuous measures with mean/median and SD/IQR as appropriate. Overall measures of usage will be presented and comparative statistics or line graphs will illustrate any changes in usage over the study duration. It is possible there may be reasons other than non-adherence which result in unused tapes (e.g. major increases or decreases in symptoms). We will collect this information at the 2 weeks clinical check, at the two telephone consultations at 6 and 12 weeks, and during the qualitative study WP3. Further prompts to encourage tape adherence will be done during the telephone consultations using the questionnaires at 6 and 12 weeks.

Adverse events (such as skin irritation, the development of new pain in other body regions thought to be related to the interventions) will be presented as the total number and proportion.

The measures of treatment efficacy, pain scale (VAS_{NA} 0-10) and the Knee Osteoarthritis & Injury Outcome Score for the patellofemoral joint (KOOS-PF) (20) will be reported with descriptive statistics and graphics at baseline, 2, 6 and 12 weeks. Preliminary analysis of all timepoints alongside the change from baseline to 12 weeks will be presented to inform the design of the future full RCT. The KOOS-PF will be scored as per validated instructions (20). This includes a "rule" that a subscale score can be calculated if 50% or more of the items in specific subscale have been completed by the participant.

The recruitment strategy will be assessed by examining the summary statistics and distribution of participants using the ethnic and socio-economic data, including the Index of Multiple Deprivation Decile. Using Census data, we will assess how participants recruited to the study reflect both the ethnic diversity of the UK population as a whole and that of Manchester and Trafford. This will inform the equality, diversity, and inclusion (EDI) recruitment strategy for the future RCT.

Qualitative assessment - WP3

An inductive thematic analysis framework will be used to analyse the data (22). This involves initial open coding of the data, applying categories to the data that identifies salient points. Patterns are then identified across the dataset to form sub-themes. Conceptually similar sub-themes are then grouped to form overarching themes. Data analysis will be undertaken by the research team. Critical discussions amongst the team, including the PPIE representative, will verify, modify and refine the themes. Reflexive field notes will feed into the analysis using NVivo software.

7. Ethical and Regulatory Considerations

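### The local ethnicity comparator leaves out Salford, a named recruitment source, and the Census comparison is not limited to the eligible age range of 40 or over

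*Protocol*

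**What the plan says.** Section 6.1 takes the Census as its data source and names the populations against which participants' ethnicity is to be judged: "both the ethnic diversity of the UK population as a whole and that of Manchester and Trafford". Its purpose follows: "This will inform the equality, diversity, and inclusion (EDI) recruitment strategy for the future RCT". No age band is given for the Census figures.

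The sources of participants are set out elsewhere:

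- Section 5.4: "Musculoskeletal physiotherapy practitioners from the Manchester Local Care Organisation (MLCO) will refer participants with PFJOA".
- Section 5.4 also lists "Participant Identification Centre: Salford Royal Hospital", and Section 5.2 likewise has participants identified "in clinics at Salford Royal Hospital".
- If the clinics do not meet recruitment, Section 5.2 adds that "an advert will be posted on the University of Manchester intranet and in the Manchester Evening News". No limit on place of residence is stated for people who respond.

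Section 5.1.1 sets the age limit: "Adults of any gender aged 40 years of age or over". There is no upper limit. The Study Summary plans 30 participants in WP2.

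**The concern.** A representativeness check compares the people recruited with a population. If the local benchmark is meant to describe the people the study could have recruited, its areas and ages should match the recruitment plan. Here the areas do not match, and the ages are left open.

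Where ethnic mix differs by area or by age, an apparent shortfall or match could partly reflect the choice of benchmark and not the recruitment strategy. A larger sample would not remove that. At stake is how the diversity result is read when recruitment to the RCT is planned.

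**Working it through.** **1. Areas, side by side (protocol text only).**

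| Area | Named as a source (5.2, 5.4) | In the local comparator (6.1) |
|---|---|---|
| Manchester | Yes (MLCO clinics; adverts) | Yes |
| Salford | Yes (Salford Royal Hospital) | No |
| Trafford | None named | Yes |

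The mismatch can be read directly from the text and needs no outside figure. The protocol has already named its areas, so this is not a detail left for the SAP.

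**2. Age.** Eligibility starts at 40. Section 6.1 names the Census as the source and says nothing on age. The reference to the whole UK sets the country against the local areas; it does not describe an age range. What can be said is that the comparator is not limited to the eligible ages.

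**3. Possible size of the Salford omission.** The protocol gives no figure to reproduce, so every share here is an assumption. Let a be the minority-ethnic share in Manchester and Trafford, s the share in Salford, and w the fraction of participants from Salford. The catchment-weighted share is (1 − w)a + ws, so adding Salford lowers the benchmark by w(a − s).

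- a = 30%, s = 20%, w = 10%: 0.10 × 10 = 1 point, or 0.3 of 30 participants.
- a = 40%, s = 20%, w = 25%: 0.25 × 20 = 5 points, or 1.5 of 30.
- a = 40%, s = 10%, w = 50%: 0.50 × 30 = 15 points, or 4.5 of 30.
- a = s = 30%: no change.

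Over a = 30-40%, s = 10-30% and w = 10-50%, the shift runs from 0 to 15 points. It never goes the other way only because these assumed values never put s above a.

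**4. Precision at n = 30.** Exact (Clopper-Pearson) 95% limits:

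- 6/30 (20%): 7.7-38.6%
- 9/30 (30%): 14.7-49.4%
- 12/30 (40%): 22.7-59.4%

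A shift of a few points is well inside these intervals.

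**5. What a benchmark that is too high would do.** Let the benchmark be a and the true share among eligible people be a − d, with a perfectly representative sample of 30. The probabilities are binomial. The ranges cover a = 20%, 30% and 40%.

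| d (assumed) | Point estimate below benchmark | Whole 95% CI below benchmark |
|---|---|---|
| 0 | about 43% | 1-2% |
| 5 points | 66-71% | 4-6% |
| 10 points | 84-93% | 12-18% |
| 15 points | 95-100% | 32-55% |

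The same figures apply whether the excess comes from area or from age. The point estimate alone is easily misread. With its interval shown, an error of 5 points seldom changes the reading, while one of 10 points or more could.

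**The case against.** The strongest reply is that Section 6.1 is silent on age, and the choice of Census table is commonly left to the SAP, which is not shown. That stands. A reader might infer that all-age Census figures will be used, but the protocol does not say so. The age limb is therefore a request to state the age range, not an error found.

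A reader might also infer that the comparison will report a false shortfall or a false match. The protocol does not support that either. It gives no ethnic shares by area or age and no expected split by source, so neither direction nor size is known. An example such as 9/30 against benchmarks of 30% and 45% does not show a changed conclusion, because the interval of 14.7-49.4% contains both.

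Three further points have weight. The UK comparison speaks to generalisability, so the Salford omission does not touch it. A hospital's location is not its patients' residence, and adverts carry no residence limit, so Manchester, Trafford and Salford together still only approximate the catchment. And the result only informs the RCT's strategy, beside other summaries that include deprivation decile; no test, threshold or row of the stop/edit/go table in Section 4.2 uses ethnicity.

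None of this explains why a named source area is missing from the local comparator.

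**Conclusion.** The point holds in a limited form. The local comparator in Section 6.1 omits Salford although Sections 5.2 and 5.4 name Salford Royal Hospital as a source, and the Census comparison is not limited to people aged 40 or over. The first part rests on the protocol's text alone and is firm. The second is a gap in specification that the SAP may already fill.

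The size is unknown. The 0 to 15 point range and the probabilities above rest wholly on assumed shares and are illustrations. A modest Salford contribution would shift the benchmark by less than the uncertainty at n = 30. The comparison is descriptive, so the consequence is confined to how the diversity result is read for the future RCT. This is a minor improvement; feasibility decisions are unaffected.

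**What to change.** In Section 6.1:

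- add Salford to the local comparator, alongside Manchester and Trafford;
- state that Census tables for ages 40 and over are used for both the local and the UK comparison;
- show the trial proportion with its 95% CI beside each benchmark.

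The cost is a sentence or so of text and a different choice of rows from public tables. No new participant data are needed. Weighting the areas by the number of people approached is not advised: it would need residence data on people who never consented, and the protocol does not describe collecting these.
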